A study was conducted by JweryAK and efficacy of clotrimazole, acetic acid and povidine iodine was compared in patients with otomycosis and it was concluded that 97.5% patients of Clotrimazole group, 72.5% of acetic acid group and 52.5% of povidine iodine group showed response to the treatment option with p value of 0.00001.³ Haq et al in a study suggested that use of clotrimazole in management of otomycosis not only relieves its symptoms but also reduces the chances of recurrent disease.⁴ As repeated daily application is difficult for the patients and results in reduced compliance so single dose application was studied. In a study conducted by Chavan et al single dose topical application of clotrimazole was done and 91.0% patients recovered at the end of 1st month with 9.0% having persistent disease.⁵ Another study conducted by Swain et al compared topical use of clotrimazole and povidine iodine solution for recurrent otomycosis. Results showed 40.90% symptoms resolution in clotrimazole group as compared to 81.81% resolution in pyodine group with p value 0.0045.⁶ Mofatteh, et al. conducted a study on 204 patients with otomycosis and compared the recovery rates between topical betadine (povidoneiodine) and clotrimazole. Authors reported the efficacy of betadine and clotrimazole was the same for the treatment of otomycosis.⁷

Due to reduced compliance of the patients and ineffective technique of using topical antifungal otomycosis has high rate of treatment failure and recurrence. Topical clotrimazole drops and povidine iodine solution have been compared for their efficacy in the past but single topical application has not been compared until now. If results are in favor of this treatment option it is convenient and cost effective. It does not requires patient compliance and numerous visits for local clinic. So it will be highly beneficial for the patient

OBJECTIVE:

To compare the efficacy of pyodine soaked gelfoam with single application of clotrimazole in otomycosis

HYPOTHESIS

Pyodine soaked gelfoam is more effective treatment option for otomycosis as compared to clotrimazole topical application

OPERATIONAL DEFINITIONS

Otomycosis

Fungal infection of external ear Canal confirmed on the basis of history and otoscopic observation of Hyphae

Treatment response

- Complete Recovery**

EAC clean with no Fungal Hyphae and return of EAC to its natural state with relief of symptoms no tragal tenderness, erythema of EAC

- Good Response:**

Dry EAC and decrease in discharge and spores

- Partial Response:**

Slight discharge/ spores but not completely dry EAC

- No Response:**

Hyper secretions in EAC

MATERIALS & METHODS:

Study design:

Randomized control trial

Study duration:

Minimum of 6 months from approval of synopsis

Settings:

Department of ENT, Benazir Bhutto Hospital Rawalpindi

Sampling technique:

Non probability, consecutive sampling

Sample Size:

Calculated via open epi Version 3

Two sided significance level $1-\alpha = 95$

Power of test (%) $1 - \beta = 80$

Ratio of sample size = 1

Percentage of clotrimazole with outcome: 41%

Percent of pyodine soaked solution with outcome = 81.81%

Odds Ratio = 6.5

Risk/prevalence ratio = 2

Risk or prevalence difference = 41

Sample size clotrimazole group = 26

Sample size pyodine group = 26

SAMPLE SELECTION

Inclusion Criteria:

- Clinically diagnosed otomycosis with intact tympanic membrane

Exclusion Criteria:

- Patients with Active Mucosal COM
- Other external auditory Canal abnormalities
- Patient having hearing aid

DATA COLLECTION PROCEDURE:

After approval from Research and Ethical Committee, Rawalpindi Medical University, Study will be carried out in the ENT department Benazir Bhutto Hospital Rawalpindi. Written informed consent will be taken from the patients for inclusion in the study. The sample size calculated is 52 patients. Individuals with a clinical otomycosis diagnosis will be recruited for the study. Individuals with active CSOM, external auditory canal abnormalities, and hearing aids will be excluded from the study. Patients will be enrolled in two treatment groups. Complete history will be taken from the patients and the ear canal to be assessed by otoscopy. The aural toilet of all patients will be done via suctioning of the ear canal. In Group A patient's ear canal will be filled with 1% clotrimazole ointment by using an Intravenous catheter and syringe. In Group B pyodine solution-soaked gel foam will be placed in the external auditory canal. Followup of patients was done on the 7th and 14th post-treatment days. Otoscopy will be performed and post-treatment symptom resolution and ear canal condition will be assessed.

DATA ANALYSIS PROCEDURE:

The collected data will be analyzed by SPSS version 23. Descriptive studies will be used to analyze qualitative and quantitative variables. Qualitative variables will be represented by

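### No local-reaction item is defined or compared by arm, and redness or tenderness is named only inside Complete Recovery, so irritation can be mistaken for incomplete response

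*Combined protocol and SAP*

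**What the plan says.** The Objective concerns efficacy alone: "To compare the efficacy of pyodine soaked gelfoam with single application of clotrimazole in otomycosis". The Hypothesis does the same.

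Under Data Collection Procedure, both arms leave material in the canal and no removal step is stated. For clotrimazole: "In Group A patient's ear canal will be filled with 1% clotrimazole ointment by using an Intravenous catheter and syringe". For pyodine: "In Group B pyodine solution-soaked gel foam will be placed in the external auditory canal". Follow-up is at days 7 and 14, and its content is one sentence: "Otoscopy will be performed and post-treatment symptom resolution and ear canal condition will be assessed".

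The Operational Definitions grade treatment response on four levels. Complete Recovery requires a clean canal without hyphae and "return of EAC to its natural state with relief of symptoms no tragal tenderness, erythema of EAC"; the natural reading is that the negative covers both tenderness and erythema. Good Response is "Dry EAC and decrease in discharge and spores". Partial Response is a canal that is not fully dry, with a little discharge or spores. No Response is "Hyper secretions in EAC". Tenderness and erythema do not appear below the top grade.

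The Data Analysis Procedure compares outcomes between groups. From the literature background to the end of that section, there is no adverse-event definition, local-reaction item, attribution rule or comparison of harm. The opening of the document was not available, so the finding of absence does not extend to it.

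**The concern.** Two things follow from this.

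First, the top grade combines fungal clearance with an uninflamed canal. An ear that has lost its hyphae but is red or sore, whether from residual disease or from the material placed in it, cannot be graded Complete Recovery. If it is dry, the nearest remaining grade is Good Response, where it is pooled with ears whose spores have only decreased. If the two materials irritate to different degrees, the comparison mixes tolerability with antifungal effect, and the grade alone cannot separate them. Randomisation does not protect against this, because the distortion arises after treatment and depends on the arm.

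Second, asking whether symptoms have resolved does not ask whether new ones have appeared. New pain, burning, rash or blockage has no defined place in the record, so the trial could report which treatment works better without describing what either does to the ear. Reactions not recorded at the visit cannot be reliably recovered later.

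**Working it through.** **1. The plan's own figure.** Inputs from Sample Size: 41% (clotrimazole), 81.81% (pyodine), two-sided 5%, 80% power, ratio 1. Gap d = 0.8181 − 0.41 = 0.4081; mean rate p̄ = 0.61405.

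- Uncorrected: n = [1.960·√(2p̄(1−p̄)) + 0.842·√(p₁(1−p₁) + p₂(1−p₂))]² / d² = (1.349 + 0.526)² / 0.1665 ≈ 21.1, so 22 per arm.
- Continuity-corrected: (n/4)·[1 + √(1 + 4/(n·d))]² = (21.1/4)·(1 + 1.210)² ≈ 25.8, so 26 per arm.

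The stated 26 per arm is reproduced and is not in dispute.

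**2. Where an irritated but cleared ear falls.**

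| Finding at visit | Complete Recovery | Good Response |
|---|---|---|
| No hyphae, dry, no redness or tenderness | yes | – |
| No hyphae, dry, red or tender | fails on inflammation | nearest fit |
| Spores reduced but present, dry | fails on fungus | fits |

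The second and third rows end in the same grade for different reasons.

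**3. How far the comparison could move.** The documents give no reaction rate, so let x be an assumed share of true recoveries downgraded for irritation.

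- If Complete and Good Response together count as success, the downgrade crosses no boundary and the shift is 0 points for any x.
- If Complete Recovery alone is the outcome, and the planning rates are taken to apply to it, the gap changes by −81.81x points (pyodine arm only), −40.81x (both arms) or +41x (clotrimazole arm only).

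| Assumed x | Pyodine rate if affected | Gap, pyodine only | Gap, both arms | Gap, clotrimazole only |
|---|---|---|---|---|
| 0 | 81.81% | 40.81 | 40.81 | 40.81 |
| 5% | 77.72% | 36.72 | 38.77 | 42.86 |
| 10% | 73.63% | 32.63 | 36.73 | 44.91 |
| 20% | 65.45% | 24.45 | 32.65 | 49.01 |

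Over 5% to 20%, the gap falls by 4.1 to 16.4 points (pyodine only), falls by 2.0 to 8.2 (both), or rises by about 2 to 8.2 (clotrimazole only).

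Power of an uncorrected two-proportion comparison at 26 per arm is Φ[(d√26 − 1.960·√(2p̄(1−p̄))) / √(p₁(1−p₁) + p₂(1−p₂))]. At x = 0 this is Φ[(2.081 − 1.349)/0.625] = 87.9%. With the pyodine arm alone affected it is 78.6%, 67.1% and 42.1% at x = 5%, 10% and 20%.

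**4. What 26 per arm can say about harm.** With 0 events in 26, the exact one-sided 95% upper limit is 1 − 0.05^(1/26) = 10.9%; the upper end of a two-sided 95% interval is 1 − 0.025^(1/26) = 13.2%. By the same power formula, assumed reaction rates of 5% and 20% in the two arms would be told apart with power of only 36.9%. Harm should therefore be described with intervals, not judged by a significance test.

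**The case against.** **An uninflamed canal is a legitimate part of recovery.** A canal that is still red and sore has not returned to normal, and the scale measures clinical response, not mycological cure. This stands, and it is why the grade should be kept and its components recorded beside it.

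**The visit record is not confined to the four grades.** Symptoms and canal condition are to be assessed, and a reaction might be noted in passing. This also stands. What is missing is a defined item, a way to tell new from residual findings, and a comparison by arm.

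**The arithmetic depends on chosen scenarios.** No grade is named as success. The background section describes the 81.81% as resolution of symptoms in an earlier study, not Complete Recovery on this scale. The calculation also assumes that irritation is unrelated to recovery and still visible at the graded visit. All of this stands: the range has to include 0 and both directions.

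A reader might also infer three stronger claims that the documents do not support.

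- *The plan intends to conclude that the foam benefits patients without harm data.* The words "So it will be highly beneficial for the patient" close the background rationale. They follow a conditional sentence about convenience and cost, and the foam is not named there; both arms are single applications. Nor does the plan propose to call either treatment safe.
- *Irritation is misread as fungal failure.* A dry, cleared but red ear falls one grade, not to No Response. That lowest grade requires no fungal finding, so irritant secretions could in principle be placed there, but nothing in the documents shows that this would happen.
- *The pyodine effect is understated by 4 to 16 points.* That is one scenario, with all the irritation placed in one arm and Complete Recovery assumed to be the outcome.

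**Conclusion.** The point holds in limited form. The text available defines no local-reaction item and plans no comparison of harm, although the arms leave different materials in the canal. Because redness and tenderness are named only within Complete Recovery, irritation can be mistaken for incomplete response.

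Neither the size nor the direction of a resulting shift can be fixed. It is 0 points if Good Response counts as success. Otherwise, under an assumed 5% to 20% downgrade, it runs from a loss of about 16 points to a gain of about 8, depending on which arm is affected. These figures are illustrations, not estimates of bias.

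The missing harm data do not depend on those assumptions. The change is worth making before enrolment because it is cheap and the information cannot be reliably reconstructed afterwards.

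**What to change.** Keep the four response grades and add the following.

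- **Record as separate items** (a) hyphae or spores, present or absent, and (b) pain, burning, redness, tenderness, rash and blocked ear. Do this at baseline, using the history and otoscopy already planned, and at days 7 and 14. The baseline record is essential: redness and tenderness may be residual disease, and without it nothing can be called new.
- **Mark at each follow-up** any reaction that is new or worse since application, with its time of onset.
- **Report by arm** the number and percentage with new or worse reactions, with exact confidence intervals, and fungal clearance beside the response grade.
- **State conclusions** as efficacy plus observed local reactions, noting that no events among 26 would still allow a true rate up to about 11% (one-sided 95%).

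The cost is a few tick-boxes, slightly longer visits and one more descriptive table. It needs no extra patients or visits and no change to either treatment.

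### Partial Response makes no comparison with entry, so an ear that is unchanged or slightly wetter can be labelled a partial response

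*Combined protocol and SAP*

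**What the plan says.** The combined protocol and SAP lists four grades under Operational Definitions, Treatment response.

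- Complete Recovery asks for a clean canal back in its natural state, with symptoms relieved.
- Good Response is "Dry EAC and decrease in discharge and spores".
- Partial Response is "Slight discharge/ spores but not completely dry EAC".
- No Response is "Hyper secretions in EAC".

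Otomycosis is defined in the same section as "Fungal infection of external ear Canal confirmed on the basis of history and otoscopic observation of Hyphae". The single inclusion criterion is "Clinically diagnosed otomycosis with intact tympanic membrane". Neither sets a threshold for discharge, wetness or spore load.

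Under Data Collection Procedure, "Complete history will be taken from the patients and the ear canal to be assessed by otoscopy", and then "The aural toilet of all patients will be done via suctioning of the ear canal". The plan does not say that discharge or spores are graded at that first otoscopy, or whether the reference state is the ear before or after suction. For the assessments, "Followup of patients was done on the 7th and 14th post-treatment days".

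The Sample Size section uses outcome rates of 41% and 81.81% but does not link the outcome to any of the four grades. The background text describes the source rates as symptom resolution.

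**The concern.** Good Response asks for a reduction, and Complete Recovery asks for a return to normal. Partial Response asks for neither: it is a condition observed on the day. An ear can already be in that condition when the patient enrols, and staying in it, or drifting into it from a drier state, earns a label that contains the word response.

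Two things are at stake. First, the frequency reported for Partial Response in each arm would mix ears that improved to slight discharge with ears that did not improve. Second, if the analysis counts Partial as success, failures move into the success column. The arm with more failures gains more from this, so the difference between arms narrows.

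**Working it through.** **Step 1. Apply the definitions as written.**

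| Ear at entry | Ear on day 14 | Grade whose text fits | Improved? |
|---|---|---|---|
| Slightly moist, spores | Same | Partial Response | No |
| Nearly dry, spores | Slightly wet, spores | Partial Response | No, worse |
| Hypersecreting | Same | No Response | No |
| Hypersecreting | Slight discharge, not dry | Partial Response | Yes |

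The first two rows are mislabelled and the last two are graded correctly. All four ears can be enrolled if hyphae are seen and the tympanic membrane is intact.

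**Step 2. Effect on the reported frequency.** If no ear changed at all, the Partial Response frequency would equal the share of ears that entered slightly moist. The documents give no baseline distribution. For assumed shares of 10%, 25%, 50% and 75%, the frequency would be 10%, 25%, 50% and 75%. At a 25% share, that is 26 × 0.25 = 6.5 ears per arm. This ignores the effect of suction.

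**Step 3. Reproduce the planned sample size.** Inputs from the Sample Size section: p1 = 0.41, p2 = 0.8181, two-sided 5%, power 80%, ratio 1. The mean rate is (0.41 + 0.8181)/2 = 0.61405 and d = 0.4081.

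- Without continuity correction: m = [1.96 √(2 × 0.61405 × 0.38595) + 0.8416 √(0.41 × 0.59 + 0.8181 × 0.1819)]² / 0.4081² = 21.1, so 22 per group.
- With correction: n = (m/4)[1 + √(1 + 4/(m d))]² = 25.8, so 26 per group, as the plan states.

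**Step 4. Dilution if Partial counts as success (illustration).** Take the design rates as true response. Let q be the fraction of failures in each arm that is graded Partial and counted as success. Then:

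- clotrimazole rate = 0.41 + 0.59q
- pyodine rate = 0.8181 + 0.1819q
- difference = 0.4081(1 − q)

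Power is exact, by enumerating both binomials at 26 per arm (two-sided 5%).

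| q (assumed) | Clotrimazole | Pyodine | Difference (points) | Power, uncorrected chi-square | Power, Fisher |
|---|---|---|---|---|---|
| 0 | 41.0% | 81.8% | 40.8 | 89% | 83% |
| 0.10 | 46.9% | 83.6% | 36.7 | 83% | 74% |
| 0.25 | 55.8% | 86.4% | 30.6 | 72% | 59% |
| 0.50 | 70.5% | 90.9% | 20.4 | 50% | 35% |

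**Step 5. When dilution does not occur.** If success is Complete Recovery, or Complete plus Good, the mislabelled ears stay among the failures. In effect q = 0, and the first row of the table applies.

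**The case against.** A reader might infer that the plan counts an unchanged ear as a responder. It does not say so. It sets no cut between response and non-response, and the only hint of what the outcome means is that the design rates describe symptom resolution, which points to something stricter than Partial. On that reading the binary comparison loses nothing. This stands, and it is why the dilution above is conditional.

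A reader might also infer that treatment failures in general are graded one level too high. Only ears that enter below hypersecretion and then stay or become slightly moist are affected, and the documents do not show how many there will be.

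A third tempting inference is that any analysis of the four-grade scale must be diluted. That has not been shown. The scale can be read as condition at the visit, and randomised arms can be compared on it: a slightly moist ear still ranks below a dry one and above a hypersecreting one, and entry state is balanced in expectation. The Data Analysis Procedure names t tests but does not say how grades would be scored, so this effect cannot be calculated from the plan.

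Finally, every ear is suctioned before treatment, so slight discharge at follow-up may have re-accumulated. This does not rescue the definition: discharge that has returned to its entry level is still not an improvement. It does limit the remedy. A heavily discharging ear that is cleaned and re-accumulates slight discharge would still be Partial Response when compared with its pre-suction state.

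**Conclusion.** The point holds as a fault in one grade definition. As written, Partial Response includes ears that are unchanged or worse, and No Response cannot take them. The reported Partial Response frequency will be misstated by however many such ears there are, and the plan gives no figure from which to estimate that number.

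The loss of between-arm difference and power (from 89% to between 83% and 50% by chi-square) rests on three assumptions: that Partial counts as success, that q lies between 0.10 and 0.50, and that q is the same in both arms. None of these comes from the documents, and neither test shown is one the plan names. The figures show sensitivity and are not a forecast. The wording should be corrected before any ear is graded, because a pre-suction state that was not recorded cannot be recovered later.

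**What to change.** 1. At the otoscopy already planned before suction, record discharge and spores separately as none, slight or marked. Record the same two items on days 7 and 14.
2. Redefine Partial Response as discharge and/or spores reduced from the pre-treatment grade but still present, with the canal not completely dry.
3. Add to No Response: a moist canal whose discharge and spores are unchanged or worse than before treatment. State how an ear is graded if one item improves and the other worsens.
4. State in the plan and the report that, because all ears are suctioned, some Partial grades in both arms may still reflect cleaning and not drug effect.

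The cost is a few lines in the definitions and two extra fields on the form. No visits, patients or staff are added, and treatment does not change. The downside is that reported response rates will look slightly less favourable.

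### The plan does not say which response grade, at which visit, is the yes/no outcome it is sized on, and its four grades leave some ears with no grade and others with two

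*Combined protocol and SAP*

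**What the plan says.** The Sample Size section is built on a yes/no event: "Percentage of clotrimazole with outcome: 41" (per cent) and "Percent of pyodine soaked solution with outcome = 81.81" (per cent), two-sided 5% significance, 80% power, 1:1, giving 26 per group. It does not name the event.

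The background, describing a cited comparison in recurrent otomycosis, states: "Results showed 40.90% symptoms resolution in clotrimazole group as compared to 81.81% resolution in pyodine group". No time point is given for those figures.

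Operational Definitions gives four grades of treatment response. Complete Recovery begins "EAC clean with no Fungal Hyphae and return of EAC to its natural state" and also requires relief of symptoms. Good asks for a dry canal with less discharge and fewer spores. Partial asks for a slight amount of discharge or spores (the two joined by a slash) in a canal that is not fully dry. No Response is defined by excess secretion alone.

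The Data Collection Procedure says "Followup of patients was done on the 7th and 14th post-treatment days" and "Otoscopy will be performed and post-treatment symptom resolution and ear canal condition will be assessed". Before suction, "Complete history will be taken from the patients and the ear canal to be assessed by otoscopy".

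The Data Analysis Procedure summarises qualitative variables by frequency and percentage, and compares the groups' outcomes by a two-sample or paired t test at p<0.05.

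**The concern.** The trial asks one efficacy question and states a hypothesis in favour of pyodine. The sample size treats the answer as a proportion, the definitions give an ordered four-level scale, follow-up adds a separate symptom assessment, and the analysis section names only t tests. No sentence connects these. If the success rule and visit are chosen after the data are seen, a reader cannot tell the planned result from the most favourable one.

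The scale adds a second problem. Otomycosis is diagnosed here as "confirmed on the basis of history and otoscopic observation of Hyphae", and every canal is suctioned at the start, so a dry canal with persisting fungus is a plausible treatment failure. That ear has no grade, and the assessor would have to place it by a private rule.

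**Working it through.** **Inputs.** From Sample Size: p1 = 0.41, p2 = 0.8181, two-sided 0.05, power 80%, 1:1, 26 per group. From Data Collection Procedure: visits at days 7 and 14. From Operational Definitions: four grades. Not in the documents, and therefore assumed: grade distributions and the correlation between visits.

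**1. The plan's own figure.** Mean rate = (0.41 + 0.8181)/2 = 0.61405; difference = 0.4081.

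n0 = [1.960·√(2 × 0.61405 × 0.38595) + 0.842·√(0.41 × 0.59 + 0.8181 × 0.1819)]² / 0.4081² = (1.349 + 0.526)² / 0.1665 ≈ 21.1.

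With continuity correction: n = (n0/4)·[1 + √(1 + 4/(n0 × 0.4081))]² = (21.1/4)·(1 + 1.210)² ≈ 25.8, so 26. The plan's figure is reproduced; the arithmetic is not at fault.

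**2. Candidate outcomes.** Success could be Complete; Complete or Good; or Complete, Good or Partial. Three cut-points × two visits = 6. Symptom resolution at two visits would add 2; those were not simulated.

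**3. Selection risk with no true difference.** Six independent tests would give 1 − 0.95⁶ = 26.5%. The six are positively correlated, so this is only an upper illustration. The simulation used 26 per arm and a four-level grade from a latent normal variable at each visit, with between-visit correlation 0.3, 0.5, 0.7 or 0.9 and 100,000 trials per setting. The assumed Complete/Good/Partial/No percentages were:
- 25/25/25/25 at both visits
- 41/20/20/19 at both visits
- 30/25/25/20, then 60/15/15/10
- 40/25/20/15, then 61/20/12/7

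| What is reported | Pearson | Fisher |
|---|---|---|
| One fixed endpoint | about 4-6% | about 0.3-3% |
| Best of six, either direction | about 20-24% | about 9-12% |
| Best of six, favouring pyodine only | about 10-12% | about 5-6% |
| Day 14 fixed, cut-point open, either direction | about 12-13% | about 5-7% |

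**4. If the planned t test were applied to scored grades.** No cut-point is needed and only the visit is open: at most 1 − 0.95² = 9.75% for two independent tests.

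**5. The grades against three ears.**

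| Ear at follow-up | Complete | Good | Partial | No Response | Result |
|---|---|---|---|---|---|
| Dry, fungus not reduced | no: fungus present | no: no decrease | no: canal is dry | no: no excess secretion | no grade |
| Cured, with discharge and spores down from baseline | yes | yes: dry and decreased | no: canal is dry | no | two grades |
| Slight discharge, unchanged | no | no: not dry | can qualify: no change required | no | called a response |

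The first row fails whether the slash in Partial means discharge alone, both, or either. The check crossed 5 baseline discharge levels, 3 baseline fungus levels, 5 follow-up discharge levels, 4 follow-up fungus levels and 2 symptom states: 5 × 3 × 5 × 4 × 2 = 600 states. Fixing follow-up at dry and counting the 3 + 2 + 1 = 6 fungus pairs with no reduction gives 5 × 6 × 2 = 60 states with no grade. These are possible states, not frequencies.

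**The case against.** The strongest defence is that the rates come from a study of symptom resolution, so symptom resolution is evidently the outcome. That explains the source of the numbers. It does not settle this trial's endpoint: the plan never adopts it, gives no visit for it, and defines treatment response by a scale on which only Complete Recovery mentions symptoms.

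A second objection is that the error rates assume deliberate selection, invented grade distributions, and Pearson or Fisher tests that the Data Analysis Procedure does not name. This stands. The figures show what the wording permits, and Fisher or a t test on scored grades gives much smaller ones.

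A third is that the grade gap is minor. This stands in part. Its frequency is unknown, and if Complete Recovery alone is primary the gaps in the lower grades touch only secondary results.

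A reader might infer more than the documents support:
- That the trial's false-positive rate is 26.5%. This needs six independent tests and selective reporting; the tests are correlated and nothing shows an intent to select.
- That the sample size is miscalculated. It reproduces exactly.
- That ungraded ears cost power or bias the comparison by a known amount. No frequency is given.
- That the outcome is defined nowhere at all. The opening part of the document was not available, so the statement covers only the background, definitions, methods and analysis text.

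**Conclusion.** The concern holds. In the text available, the yes/no outcome behind 41% against 81.81% has no stated success rule and no deciding visit. The grading scale fails on its own wording in three ways: one kind of ear has no grade, one can have two, and one can be called a response without having changed.

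The selection risk is conditional on the most favourable of six endpoints being reported and on the assumed grade distributions: about 20-24% (Pearson) or 9-12% (Fisher) two-sided, and about half that in pyodine's favour. If scored grades were compared by t test, the limit is 9.75%. The grading faults follow from the wording and need no assumption, but their effect on results cannot be sized. The outcome should be fixed before data are seen, since a later choice would not be credible.

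**What to change.** 1. Before data are seen, name one binary primary outcome at one visit, for example Complete Recovery as already defined, at day 14. Count every other randomised patient as not recovered, compare the two proportions, and report the other grades, symptom resolution and day 7 as secondary.
2. State that an ear with hypersecretion is always No Response, that otherwise each ear gets the highest grade it meets, and that No Response is the residual grade for any ear not meeting Complete, Good or Partial. Each ear then has exactly one grade by construction, once item 3 is settled.
3. State one reading of the slash in Partial (for example, either finding present). Require for Partial a reduction from the otoscopy before suction, and record discharge and hyphae or spores at that examination. Say also how an ear already dry at that examination is judged on the discharge part of Good, since it has no discharge to lose.

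**Cost.** A few sentences and two baseline form items; the baseline otoscopy is already planned and no visit is added.

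The real downside is power. The 80% for 26 per group rests on symptom-resolution rates, and the documents give none for Complete Recovery, a stricter outcome. The power should be restated as resting on symptom resolution or rechecked for the chosen outcome. For scale, under assumed falls: if both rates were 10, 20 or 30% lower in relative terms, the formula in step 1 gives 33, 42 or 53 per arm. If both fell by 5 to 20 points with the gap kept, 26 per arm would still give 84-87% power by Pearson and 78-81% by Fisher.

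### The planning effect comes from recurrent otomycosis, but the trial enrols any otomycosis and plans one unadjusted comparison, so effect size and power may depend on an unplanned case mix

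*Combined protocol and SAP*

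**What the plan says.** Under Sample Selection, the only inclusion criterion is "Clinically diagnosed otomycosis with intact tympanic membrane". The exclusions, restated under Data Collection Procedure, do not concern disease history: "Individuals with active CSOM, external auditory canal abnormalities, and hearing aids will be excluded from the study". Sampling is "Non probability, consecutive sampling". On allocation, the procedure says only "Patients will be enrolled in two treatment groups". A full history is to be taken, but no use of it as a stratum or covariate is described. Data Analysis Procedure gives one overall two-group comparison, without adjustment, subgroup or interaction.

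The Sample Size section uses 41% for clotrimazole and 81.81% for pyodine. These match the introduction's study that "compared topical use of clotrimazole and povidine iodine solution for recurrent otomycosis", which found 40.90% v 81.81%; its title in the reference list says recalcitrant disease. The introduction cites two other comparisons of these agents, both in patients described simply as having otomycosis. In one, "97.5% patients of Clotrimazole group, 72.5% of acetic acid group and 52.5% of povidine iodine group showed response". In the other, of 204 patients, the "efficacy of betadine and clotrimazole was the same for the treatment of otomycosis". A single-arm study of one clotrimazole application is cited with 91.0% recovery at one month.

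The hypothesis is that pyodine-soaked gelfoam is the more effective option for otomycosis, with no restriction to recurrent disease.

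**The concern.** The effect on which the trial is sized is borrowed from a narrower population than the one it will enrol. The cited clotrimazole response is 40.90% in the recurrent-disease study, against 91.0% and 97.5% in the studies not so described. If history explains even part of that gap, recurrence is strongly prognostic and may also change the size of the treatment difference.

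Two things are at stake. First, the 80% power holds only if enrolled patients respond like the recurrent-disease source. Second, the pooled result would be hard to interpret. A null finding could reflect a diluted effect, and a positive one could come mainly from recurrent cases yet be reported as a finding about otomycosis in general. As planned, the analysis could not tell these apart, because case mix is neither classified nor used.

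**Working it through.** **1. Reproduce the plan's figure.** Inputs from Sample Size: 41%, 81.81%, two-sided 5%, 80% power, ratio 1.

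- Mean rate = (0.41 + 0.8181)/2 = 0.614; difference d = 0.4081.
- Uncorrected n = [1.96√(2 × 0.614 × 0.386) + 0.842√(0.41 × 0.59 + 0.8181 × 0.1819)]² / 0.4081² = 21.1, so 22 per arm.
- With continuity correction, n = (21.1/4) × [1 + √(1 + 4/(21.1 × 0.4081))]² = 25.8, so **26 per arm**.

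This matches the plan exactly. At 26 per arm and these rates, power is 88% by the uncorrected formula and 83% by exact enumeration of Fisher's test (the latter at 40.90% v 81.81%). The arithmetic is sound for a population that responds like the recurrent-disease study.

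**2. Let the case mix vary.** Let s be the recurrent share, and let recurrent cases respond at 40.90% v 81.81%. Let non-recurrent cases respond at c on clotrimazole and q on pyodine. Then:

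- clotrimazole rate = 40.90s + c(1 − s)
- pyodine rate = 81.81s + q(1 − s)
- difference = 40.91s + (q − c)(1 − s)

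The documents give neither s nor any rates for first-episode disease, so both are assumptions shown as a range. *Scenario A* sets c and q to 97.5% and 52.5%. *Scenario B* takes the equal-efficacy finding with a common rate of 91%. That rate is assumed: the cited 91.0% is for clotrimazole alone, at one month.

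Power at 26 per arm = Φ{[|D|√26 − 1.96√(2p̄(1 − p̄))] / √(p₁(1 − p₁) + p₂(1 − p₂))}, where p₁ and p₂ are the two mixed rates, p̄ their mean and D their difference. Fisher power is in brackets. Needed n is continuity-corrected, for 80% power.

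| Recurrent share | A: difference, power | B: difference, power | B: n per arm needed |
|---|---|---|---|
| 100% | +40.9 points, 88% (83%) | +40.9 points, 88% (83%) | 26 |
| 75% | +19.4, 31% (23%) | +30.7, 68% (58%) | 41 |
| 50% | −2.0, 4% (3%) | +20.5, 41% (29%) | 77 |
| 25% | −23.5, 47% (35%), favouring clotrimazole | +10.2, 17% (9%) | 224 |

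Worked cell (B, 50%): clotrimazole 0.5 × 40.90 + 0.5 × 91 = 65.95%; pyodine 0.5 × 81.81 + 0.5 × 91 = 86.4%; difference 20.5 points. Power = Φ[(0.2046 × 5.10 − 1.96 × 0.602)/0.585] = Φ(−0.24) = 41%.

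In A the difference is zero at s = 45.0/(45.0 + 40.91) = 52.4%. In B it never changes sign. With a common rate of 70% instead of 91%, the 50% row of B gives power of 34% (26%) and 93 per arm needed.

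**3. Chance imbalance.** With 26 per arm and half the patients recurrent, the between-arm difference in recurrent share has a standard deviation of √(2 × 0.25/26) = 0.139, about 14 points. The planned analysis has no means of adjusting for it.

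**The case against.** A reader might infer that the plan's own sources show opposite treatment effects in first-episode and recurrent disease. The documents do not support that. No cited study is described as first-episode; the contrast is between recurrent otomycosis and otomycosis not further described, which may include recurrent cases. The reversal rests on one study. With the equal-efficacy study the effect is diluted, not cancelled.

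There are also competing explanations. By its title, the recurrent-disease study used gelfoam, the vehicle in Group B, and the other two comparisons are not described that way. The introduction says earlier comparisons were of drops and solution and that single application had not been compared. Outcomes are variously symptom resolution, response and recovery, and the 91.0% is at one month while this trial looks at days 7 and 14. All of this stands, so effect modification by recurrence is possible but not shown.

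Two further inferences also fail. It is tempting to say that patients who failed clotrimazole will be re-exposed to an agent that does not work for them. But the plan attributes failure and recurrence to poor adherence and faulty application, and nothing says the recurrent-disease study enrolled clotrimazole failures. It is also tempting to call chance imbalance in recurrent cases a bias. Under randomisation it costs precision; the pooled comparison still estimates the average effect in the enrolled mix, which fits an objective framed as otomycosis in general.

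What the objection does not remove is the mismatch between the population behind the planning rates and the population enrolled, or the inability of the planned analysis to show whether it mattered.

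**Conclusion.** The concern holds in a limited form. The sample size is correct arithmetic on rates from recurrent disease, applied to a trial open to all clinically diagnosed otomycosis, with one unadjusted comparison. Recurrence or prior treatment is plausibly prognostic and may modify the effect. The estimate is not biased for the enrolled mix, but its size and the power may depend on a recurrent share that nobody has planned for.

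The size is illustrative only. It rests on recurrent cases behaving like the recurrent-disease study and on assumed rates for everyone else. On the milder assumption (equal efficacy), a half-recurrent sample halves the difference to about 20 points and leaves power of 34% to 41% (Fisher 26% to 29%), depending on the common rate. On the harsher one, the difference vanishes near 52% recurrent. This is an inexpensive improvement worth making before enrolment, not a flaw that invalidates the design.

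**What to change.** - From the history already taken, record at entry whether the case is a first episode or is recurrent or previously treated with a topical antifungal.
- Stratify randomisation by this item.
- Make the overall treatment difference, adjusted for stratum, the main comparison.
- Report the treatment-by-stratum estimate with confidence intervals, as supportive only. Do not base conclusions on significance within one stratum: with an even split (13 per arm per stratum), even 41% v 82% would be detected only about 48% of the time by Fisher's test.
- Report the enrolled case mix beside the conclusion.
- State in Sample Size that 80% power applies only if enrolled patients respond like the recurrent-disease source.

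The cost is one entry item, two randomisation lists, and by-stratum estimates that will be imprecise with 52 patients. The stratification has to be in place before the first patient is randomised, because it cannot be added afterwards.
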